10.5 Missing Data

In general, no imputation of missing values will be done except for the following:

- For SARS-CoV-2 RBD of S protein antibodies, and viral neutralizing antibodies, concentration values marked as below the lower limit of quantification (LLOQ) will be set to 0.5*LLOQ for computation purposes.
- Imputation of (partially) missing AE start dates:
 - If start date year value is missing, the date uncertainty is too high to impute a rational date. Therefore, if year value is missing, the imputed AE start date is set to missing.
 - If start date year value is before the vaccination start date year value, then the AE started before the vaccination. Therefore:
 - If month is missing, the imputed start date is set to the mid-year point (i.e., 01JULYYYY).
 - If month is not missing, the imputed start date is set to the mid-month point (i.e., 15MONYYYY).
 - If start date year value is equal to the vaccination start date year value, the start date month needs to be compared against the vaccination start date month, to determine the imputation rule to apply. Therefore:
 - If month is missing, the imputed month and imputed day is the same as start of vaccination
 - If month is lower than vaccination start date month and start date day is missing, the imputed start date is set to the mid-month point (i.e. 15MONYYYY).
 - If month is equal to the vaccination start date month and start date day is missing, the start day will be set to the start day of vaccination.
 - If month is greater than the vaccination start date month and start date day is missing, the imputed start date is set to the beginning of the month (i.e., 01MONYYYY).
 - If start date year value is greater than the vaccination start date year value, the AE started after vaccination. Therefore:
 - If month is missing, the imputed start date is set to the year start point (i.e., 01JANYYYY).
 - If start date month is not missing and start date day is missing, the imputed start date is set to the beginning of the month (i.e., 01MONYYYY).
 - If after imputation of start and resolution date (see below) a start date is after the resolution date (for example if a missing day of a start date is set to 15 and the resolution date is before the 15th of the same month and year) then the start date will be set to the resolution date.
- Imputation of (partially) missing AE end dates:

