 - If date of resolution is completely missing, and it is assumed that it resolved at the date of the end of the trial, the date of the end of the trial is used as the AE end date.
 - If year is present, it is assumed that it resolved on 31 December of that year (i.e., 31DECYYYY), or at the end of the trial if this is earlier and in the same year.

- If year and month are present, it is assumed that it resolved on the last day of that month, or at the end of the trial if this is earlier and in the same month/year.
- Imputation of missing AE start times:
 - If the (recorded or imputed) AE start date is equal to the vaccination start date, then the AE start time will be the time of vaccination start.
 - In all other cases, AE start time will be imputed as 00:00.

If not stated otherwise, the original or incomplete data will be presented in listings rather than the imputed one.

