10.7.1 Treatment Emergent Adverse Events (TEAEs)

A TEAE is any AE that first occurs or increases in severity or relationship to trial vaccine after the first dose of vaccine. AEs which change in severity or relationship to trial vaccine are assigned a new start date and captured as a new record in the CRF. Hence, an AE is defined as TEAEs if the start date/time is after the date/time of first vaccination. Imputed AE start date/time as defined in Section 10.5 will be considered when assessing if an AE is treatment emergent. If the AE start date is still missing after applying imputation rules (i.e. missing year), the AE will be considered treatment emergent.

All Solicited AEs are considered treatment emergent, even in the case that (partially) missing or conflicting date/time information is recorded or imputed.

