10.7.2 Solicited Adverse Events

Solicited systemic AEs (fever, headache, fatigue, chills, myalgia, arthralgia, nausea/vomiting, and diarrhea) will be recorded from Day -7 until Day -1 using a paper diary. These records shall provide a baseline for reactogenicity and safety for each enrolled subject. See Table 5.

Solicited local AEs (injection site pain, redness, swelling, and itching) and solicited systemic AEs will be recorded on the days of vaccination (Day 1 and Day 29) and the following 7 days using a paper diary. See Table 6.

Body temperature should be measured orally and by using the thermometer provided to the subject at Visit 1.

Solicited AEs will be assessed on an intensity scale of absent, mild, moderate, and severe (5 and 6). In case of related Grade 3 solicited or unsolicited AEs reported for more than 1 day in the diary, the subject will be questioned to establish the total duration of the AE as exactly as possible and this information will be recorded in the eCRF.

Solicited systemic Grade 3 AEs and unsolicited Grade 3 AEs, except for solicited injection site reactions, must be reported to the medical monitor without delay, on the same day of awareness by the site.

By definition, all solicited local AEs occurring from the time of first vaccination are considered related to trial vaccination. For solicited systemic AEs, the Investigator will assess the relationship between trial vaccine and each occurrence of each AE.

Table 5 Intensity Grading for Solicited Local Adverse Events

Adverse Event	Grade	Definition
Pain at injection site	0	Absent
	1	Does not interfere with activity
	2	Interferes with activity and/or repeated use of non-narcotic pain reliever >24 hours
	3	Prevents daily activity and/or repeated use of narcotic pain reliever
Redness	0	<2.5 cm
	1	2.5 – 5 cm
	2	5.1 – 10 cm
	3	>10 cm
Swelling	0	<2.5 cm
	1	2.5 – 5 cm and does not interfere with activity
	2	5.1 – 10 cm or interferes with activity
	3	>10 cm or prevents daily activity
Itching	0	Absent
	1	Mild, no interference with normal activity
	2	Moderate, some interference with normal activity
	3	Significant, prevents normal activity

Based on the United States Food and Drug Administration toxicity grading scale [5].

Table 6 Intensity Grading for Solicited Systemic Adverse Events

Adverse Event	Grade	Definition
Fever	0	<38°C
	1	≥38 – 38.4°C
	2	≥38.5 – 38.9°C
	3	≥39°C
Headache	0	Absent
	1	Mild, no interference with normal activity

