12.7.1.1 Analysis of Unsolicited AEs and Solicited AEs

An overall summary of unsolicited AEs will be prepared for AEs occurring within 28 days after each dose, within 28 days after any dose, and all reported AEs (including those reported at more than 28 days after any dose).

- Unsolicited AEs
- Related unsolicited AEs
- SAEs (includes solicited AEs)
- Related SAEs (includes solicited AEs)
- Grade 3 (severe) unsolicited AEs
- Grade 3 (severe) related unsolicited AEs
- Intercurrent medical conditions affecting immune response (includes solicited AEs)
- Medically attended AEs (includes solicited AEs)
- Related medically attended AEs (includes solicited AEs)
- AESIs (includes solicited AEs)
- Related AESIs (includes solicited AEs)
- Medically attended AEs (includes solicited AEs)
- Related medically attended AEs (includes solicited AEs)
- AESIs (includes solicited AEs)
- Related AESIs (includes solicited AEs)
- AEs leading to vaccine withdrawal
- AEs leading to withdrawal from trial

The overall summary will also be presented for overall and by sex (female/male)* and for any dose (dose 1 and dose 2) and include AEs for the duration of the trial.

The following summaries of unsolicited AEs by SOC and PT will further be provided, separately for AEs occurring within the first 28 days after each vaccination, within the 28 days after any vaccination, and all reported AEs (including those reported at more than 28 days after any dose) if not otherwise stated:

- Occurrence of unsolicited AEs
- Occurrence of related unsolicited AEs*
- Occurrence of SAEs (includes solicited AEs)*
- Occurrence of related SAEs (includes solicited AEs) *
- Occurrence of unsolicited AEs by maximum severity (mild / moderate / severe)*
- Occurrence of related unsolicited AEs by maximum severity (mild / moderate / severe) *
- Occurrence of SAEs by maximum severity (mild / moderate / severe) (includes solicited AEs)*

- Occurrence of related SAEs by maximum severity (mild / moderate / severe) (includes solicited AEs)*
- Occurrence of AESIs (includes solicited AEs)
- Occurrence of related AESIs (includes solicited AEs)*
- Occurrence of intercurrent medical conditions affecting immune response (includes solicited AEs)*
- Occurrence of medically attended AEs (includes solicited AEs)*
- Occurrence of related medically attended AEs (includes solicited AEs)*
- Occurrence of AEs leading to withdrawal from trial (includes solicited AEs)

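### The treatment-emergent flag fails unsolicited AEs whose start is imputed to the vaccination time and, read literally, takes in baseline solicited entries; the exposure is in AE outputs with no lower time bound

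*SAP*

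**What the plan says.** **The flag.** SAP 10.7.1 gives the working definition: "an AE is defined as TEAEs if the start date/time is after the date/time of first vaccination". It adds that "Imputed AE start date/time as defined in Section 10.5 will be considered when assessing if an AE is treatment emergent". An AE whose year is missing is treated as treatment emergent. A separate sentence covers solicited events: "All Solicited AEs are considered treatment emergent, even in the case that (partially) missing or conflicting date/time information is recorded or imputed".

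**The imputation.** SAP 10.5 handles an incomplete AE start as follows:
- Vaccination month known, day missing: "the start day will be set to the start day of vaccination".
- Vaccination year known: "If month is missing, the imputed month and imputed day is the same as start of vaccination".
- Start date, recorded or imputed, equal to the vaccination date, with no time: "then the AE start time will be the time of vaccination start".
- Time missing on any other date: midnight.

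**Data before vaccination.** Under SAP 10.7.2, solicited systemic AEs "will be recorded from Day -7 until Day -1 using a paper diary" and serve as each subject's baseline. SAP 10.7.3 has unsolicited AEs collected by diary in the same week.

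**The outputs.** SAP 12.7.1.1 plans summaries for the 28 days after each dose, for the 28 days after any dose, and for "all reported AEs (including those reported at more than 28 days after any dose"). Appendix 4 keeps the overall summary (Table 14.3.2.1.1) and several Duration of Trial tables, including Table 14.3.2.17.1 for unsolicited AEs.

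**The concern.** The definition uses a strict inequality, and the imputation produces exact equality. An unsolicited AE imputed to the moment of vaccination therefore fails the test, although nothing in its record shows that it began before the dose. The solicited sentence has the opposite fault. It has no lower time limit, so it covers diary entries that the SAP itself calls baseline.

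This matters because AEs are recorded before the first dose and the subjects serve as their own controls. Some rule must separate events before vaccination from events after it. The windowed tables do so through their day windows. The all-reported and Duration of Trial outputs state no starting point, and 10.7.1 is the only rule in the SAP that could supply one. Unsolicited AEs, SAEs and AESIs are primary safety endpoints.

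**Working it through.** The plan gives no figure to reproduce, so the check applies the two sections to each kind of incomplete date.

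**Inputs.** V is the date and time of first vaccination, which is how I read the vaccination start date in 10.5. S is the AE start after the 10.5 imputation. For illustration V is 12 May 2021, 10:00. That date is an assumption, and the ties do not depend on it. No AE is assumed to have a resolution date before V.

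**Rule as written (10.7.1).** Treatment emergent if S > V, or if the year is missing, or if the AE is solicited.

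**Alternative.** Replace S > V by S ≥ V.

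| Recorded start of an unsolicited AE | S after imputation | S > V | S ≥ V |
|---|---|---|---|
| Vaccination day, time missing | 12 May 2021 10:00 | no | **yes** |
| Vaccination month, day missing | 12 May 2021 10:00 | no | **yes** |
| Vaccination year, month missing | 12 May 2021 10:00 | no | **yes** |
| Later month, day missing | 1 June 2021 00:00 | yes | yes |
| Earlier month, day missing | 15 April 2021 00:00 | no | no |
| Later year, month missing | 1 January 2022 00:00 | yes | yes |
| Earlier year, month missing | 1 July 2020 00:00 | no | no |
| Year missing | none | yes, by rule | yes, by rule |
| Next day, time missing | 13 May 2021 00:00 | yes | yes |
| Vaccination day, 14:00 recorded | 12 May 2021 14:00 | yes | yes |
| Vaccination day, 08:00 recorded | 12 May 2021 08:00 | no | no |
| Day -3, time missing | 9 May 2021 00:00 | no | no |

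Three of the 12 patterns have S = V and fail. Under S ≥ V those three pass and the other nine are unchanged. The ordering as written is also perverse: with only the vaccination year known, the AE is not treatment emergent, but with even the year missing it is.

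**Solicited events.** A systemic diary entry on Day -3 has S < V and fails the date test. The sentence on solicited AEs then makes it treatment emergent. A narrower wording was available: in 10.7.2, automatic relatedness of local reactions is limited to events from first vaccination onward.

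**Which outputs depend on the flag.**
- *Solicited tables* 14.3.2.2.1, 14.3.2.3.1, 14.3.2.4.1 and 14.3.2.6.1 cover the vaccination day and the next 7 days. They do not need the flag.
- *Unsolicited tables* 14.3.2.16.1 to .3 and 14.3.2.20.1 to .3 cover the vaccination day and the next 28 days. They do not need it either.
- *The all-reported part of Table 14.3.2.1.1, and Table 14.3.2.17.1,* have no lower bound. With the flag, the three tied patterns are lost. Without it, unsolicited AEs from before the dose enter.

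**Scale of one subject.** With 129 enrolled (SAP 6.3), one subject moves an overall percentage by at most about 1/129 = 0.8 points if all are in the safety set. If the seven co-morbidity strata were equal and did not overlap (an assumption), each would hold 129/7 ≈ 18 subjects, and one subject would move a stratum by 7/129 ≈ 5 points. Real strata overlap and will be uneven, so the step will be smaller in some and larger in others.

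**The case against.** The strongest reply is that no analysis in SAP 12.7 and no output title in Appendix 4 is restricted to treatment-emergent AEs. The endpoint for unsolicited AEs is defined on the vaccination day and the following 28 days, and the tables that carry it use that window. An AE dated or imputed to Day 1 stays in them unless a programmer adds a filter that the documents do not call for. The table shells are a separate document. This stands. A reader might infer that vaccination-day AEs drop out of the primary safety tables, but the documents show a fault in the flag and no loss from those tables.

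A reader might also infer that baseline solicited entries inflate the reactogenicity results. That is not supported. The solicited tables start on the vaccination day, and Listing 16.2.7.4 shows the Day -7 to Day -1 entries separately. SAP 12.7.1 excludes solicited AEs from unsolicited summaries unless otherwise stated, so the solicited sentence cannot inflate Table 14.3.2.17.1. The rows of the overall summary that do include solicited AEs, such as SAEs and medically attended AEs, leave only a narrow route.

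Two other Duration of Trial tables are less exposed to pre-vaccination events. Table 14.3.2.17.2 is limited to related AEs, which largely excludes events before any dose. Table 14.3.2.26.1 covers AESIs, whose collection in the protocol's Schedule of Activities starts on Day 1.

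It can also be said that *after* was meant loosely. SAP 10.6 counts against this: it uses *on or after* first dosing for concomitant medication. A programmer following 10.7.1 would code a strict inequality.

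**Conclusion.** The concern holds as an inconsistency between two sections of the SAP that can reach a limited set of outputs. The flag as written fails unsolicited AEs in three patterns of incomplete date, and its solicited sentence literally includes baseline diary entries. The windowed 7-day and 28-day tables are not affected as titled. The all-reported part of Table 14.3.2.1.1 and Table 14.3.2.17.1 are exposed whether or not the flag is applied, because both choices give an unwanted result.

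The number of AEs affected cannot be derived. The documents give no frequency of untimed Day 1 AEs, of partial dates, or of unsolicited AEs before vaccination, so any percentage loss would be a guess. The conclusion assumes that *after* is coded as written and that the separate shells do not already settle which AEs these outputs include. The trial is descriptive and the correction is nearly free, so it should be made before the safety tables are programmed.

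**What to change.** 1. In SAP 10.7.1, define a treatment-emergent AE as one starting *on or after the date/time of first vaccination*, so that starts imputed to the vaccination time count.
2. Limit the sentence on solicited AEs to diary entries from first vaccination onward. Day -7 to Day -1 entries then remain baseline, as 10.7.2 intends.
3. In SAP 12.7.1.1 and Appendix 4, state that the all-reported and Duration of Trial AE tables count treatment-emergent AEs only, and list pre-vaccination AEs separately.

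The cost is a few sentences and one derivation flag. Item 3 narrows what 12.7.1.1 now calls all reported AEs, so the output labels should say so. Item 1 has a small downside: some untimed Day 1 AEs that began before the dose will be counted, which errs on the conservative side. The existing rule in 10.5 that moves a start back to the resolution date, when imputation would place it later, still keeps out AEs known to have ended before the vaccination day.

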10.7.2 Solicited Adverse Events

Solicited systemic AEs (fever, headache, fatigue, chills, myalgia, arthralgia, nausea/vomiting, and diarrhea) will be recorded from Day -7 until Day -1 using a paper diary. These records shall provide a baseline for reactogenicity and safety for each enrolled subject. See Table 5.

Solicited local AEs (injection site pain, redness, swelling, and itching) and solicited systemic AEs will be recorded on the days of vaccination (Day 1 and Day 29) and the following 7 days using a paper diary. See Table 6.

Body temperature should be measured orally and by using the thermometer provided to the subject at Visit 1.

Solicited AEs will be assessed on an intensity scale of absent, mild, moderate, and severe (5 and 6). In case of related Grade 3 solicited or unsolicited AEs reported for more than 1 day in the diary, the subject will be questioned to establish the total duration of the AE as exactly as possible and this information will be recorded in the eCRF.

Solicited systemic Grade 3 AEs and unsolicited Grade 3 AEs, except for solicited injection site reactions, must be reported to the medical monitor without delay, on the same day of awareness by the site.

By definition, all solicited local AEs occurring from the time of first vaccination are considered related to trial vaccination. For solicited systemic AEs, the Investigator will assess the relationship between trial vaccine and each occurrence of each AE.

Table 5 Intensity Grading for Solicited Local Adverse Events

Adverse Event	Grade	Definition
Pain at injection site	0	Absent
	1	Does not interfere with activity
	2	Interferes with activity and/or repeated use of non-narcotic pain reliever >24 hours
	3	Prevents daily activity and/or repeated use of narcotic pain reliever
Redness	0	<2.5 cm
	1	2.5 – 5 cm
	2	5.1 – 10 cm
	3	>10 cm
Swelling	0	<2.5 cm
	1	2.5 – 5 cm and does not interfere with activity
	2	5.1 – 10 cm or interferes with activity
	3	>10 cm or prevents daily activity
Itching	0	Absent
	1	Mild, no interference with normal activity
	2	Moderate, some interference with normal activity
	3	Significant, prevents normal activity

Based on the United States Food and Drug Administration toxicity grading scale [5].

Table 6 Intensity Grading for Solicited Systemic Adverse Events

Adverse Event	Grade	Definition
Fever	0	<38°C
	1	≥38 – 38.4°C
	2	≥38.5 – 38.9°C
	3	≥39°C
Headache	0	Absent
	1	Mild, no interference with normal activity
	2	Moderate, some interference with normal activity and/or repeated use of non-narcotic pain reliever >24 hours
	3	Significant; any use of narcotic pain reliever and/or prevents daily activity
Fatigue	0	Absent
	1	Mild, no interference with normal activity
	2	Moderate, some interference with normal activity
	3	Significant, prevents normal activity
Chills	0	Absent
	1	Mild, no interference with normal activity
	2	Moderate, some interference with normal activity
	3	Significant, prevents normal activity
Myalgia	0	Absent
	1	Mild, no interference with normal activity
	2	Moderate, some interference with normal activity
	3	Significant, prevents normal activity
Arthralgia	0	Absent
	1	Mild, no interference with activity
	2	Moderate, some interference with activity
	3	Significant, prevents activity
Nausea/ Vomiting	0	Absent
	1	Mild, no interference with activity and/or 1 – 2 episodes/ 24 hours
	2	Moderate, some interference with activity and/or >2 episodes/ 24 hours
	3	Significant, prevents daily activity, requires outpatient intravenous hydration
Diarrhea	0	Absent
	1	2 – 3 loose stools
	2	4 – 5 stools
	3	6 or more watery stools/over 24 hours or requires outpatient intravenous hydration

Based on the United States Food and Drug Administration toxicity grading scale [5].

10.7.2.1.1 Duration of Solicited Adverse Events

Duration of solicited local and systemic adverse events are defined as the sum consecutive days with local/systemic adverse events (days 1 to 8) for the same grade. For example, Fatigue with grade 1 occurring on day 2 and 3 and day 7 will be counted as two separate events with the duration 2 days and 1 day. For the duration of solicited local and systemic AEs ongoing beyond Day 8 the following definition is used:

If the AE is present on day 8 in the diary and the same AE is present on day 9 on the eCRF, the sum of days between the date of day 9 and end date for the AE on the eCRF is added to the consecutive days as collected on the diary. If the duration of any AE continues after the next dose and the subject experience an AE of the same type in the second dose, these two events will be presented separately.

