### 10.3.5 Primary Analysis

#### 10.3.5.1 Primary Safety Analysis

The safety measurements will include:

2. AEs (type, intensity, frequency and relationship to trial vaccination), i.e., incidence and severity of AEs for both solicited local (injection site pain, redness, swelling, and itching) and solicited systemic events (fever, headache, fatigue, chills, myalgia, arthralgia, nausea/vomiting, and diarrhea) occurring on the day of vaccination and the following 7 days, and unsolicited events (occurring on the day of vaccination and the following 28 days).
3. SAEs and AESIs throughout the trial.

**Solicited AEs:** For reactogenicity assessment, the number and percentage of subjects with at least 1 solicited AE of any kind, by severity grade, for local, systemic, and overall, will be summarized after the first vaccination and after the second vaccination. For subjects with more than 1 episode of the same event, the maximum severity will be used for tabulations. In addition, the frequencies and severity of each solicited AE will be summarized for each vaccination day and the following 7 days. Similar tabulations will be

performed for solicited systemic AEs considered as related to the trial vaccine. The duration and severity of solicited AEs will be analyzed at subject level.

In addition, other indicators of safety (e.g., body temperature) will be collected and summarized. The number and percentage of subjects with Grade 3 adverse reaction(s) or SAEs considered as related to the trial vaccine according to the Investigator with the 95% CI based on the Beta (0.5, 0.5) prior distribution will be calculated and summarized.

**Unsolicited AEs:** Unsolicited AEs, SAEs and AESIs will be coded using the Medical Dictionary for Regulatory Activities (MedDRA) by System Organ Class (SOC) and Preferred Term (PT). The frequency and percentage of subjects reporting these events will be tabulated at the SOC and PT levels. Additional similar tabulations will be performed to evaluate severity and relationship to the trial vaccine. AEs that are reported as related to the trial vaccine will be considered trial vaccine-related; missing classifications concerning trial vaccine relationship will also be considered trial vaccine-related.

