9.4 Estimands

Based on the Protocol Amendment #1, a subset of endpoints will be presented. See Section 6.1, 6.2, 6.3 and 6.4 and Appendix 4 List of Abbreviated Scope Based on SAP Version 2.0 for additional details.

ENDPOINTS (subject level)	ESTIMANDS (population level)
Primary Safety	

The frequency, intensity, and duration of solicited local AEs on each vaccination day and the following 7 days.
 
The frequency, intensity, duration, and relationship to trial vaccination of solicited systemic AEs on each vaccination day and the following 7 days.
 
The occurrence, intensity and relationship to trial vaccination of unsolicited AEs on each vaccination day and the following 28 days.
 
The occurrence and relationship to trial vaccination of SAEs and AESIs throughout the trial.
	
In subjects who received at least one dose of CVnCoV vaccine and a post baseline vaccine safety assessment is available. Subjects receiving an authorized/licensed COVID-19 vaccine during the course of the trial will be censored at the day after intake. The primary safety will be analyzed with the safety analysis set.
 
The number and percentage of subjects overall and by co-morbidity:
 
Each solicited local AE within 7 days (after each trial vaccination by intensity and overall).
 
Each solicited systemic AE within 7 days after each trial vaccination by intensity, by relationship to trial vaccine and overall.
 
The mean duration in days by group with standard deviation of solicited AEs (within the solicited period, total duration).
 
At least 1 unsolicited AEs, at least 1 grade unsolicited AEs and each unsolicited AEs by SOC/PT occurring within 28 days after each trial vaccination and overall by causal relationship to trial vaccine and overall.
 
At least 1 SAE, or at least 1 AESI to vaccine overall by causal relationship to trial vaccine and overall.

ENDPOINTS (subject level)	ESTIMANDS (population level)
Primary Immunogenicity	

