12.7.1.2 Analysis of Solicited AEs

The following summaries of solicited AEs within 7 days after each trial vaccination and within 7 days after any trial vaccination will be provided. If not stated otherwise the maximum grade will be presented (grade 0 to grade 3).

- Summary of solicited AEs, local AEs and systemic AEs, overall and by maximum grade
- Summary of local AEs, overall and by maximum grade
- Summary of systemic AEs, overall and by maximum grade (occurrence of systemic AEs will also be presented from day -7 until day -1)*
- Summary of related systemic AEs, overall and by maximum grade*
- Duration (days) of solicited AEs, overall and for Grade 3 events
- Duration (days) of local AEs, overall and for Grade 3 events*
- Duration (days) of systemic AEs, overall and for Grade 3 events*
- Duration (days) of related systemic AEs, overall and for Grade 3 events*
- Daily summary of local AEs (only for each dose)*
- Daily summary of systemic AEs (only for each dose)*
- Daily summary of related systemic AEs (only for each dose)*
- Summary of time of onset (Day) for grade 3 solicited AEs, any solicited AEs, local, systemic AEs, and related systemic AEs*
- Time of onset (Day) of local AEs*
- Time of onset (Day) of systemic AEs*
- Time of onset (Day) of related systemic AEs*
- Individual grade 3 solicited local and systemic adverse events will be presented in a figure.*

In addition, number and percentage of subjects with solicited Grade 3 adverse reaction(s) or SAEs considered as related to the trial vaccine according to the Investigator with the 95% credibility interval based on the Beta (0.5, 1.5) prior distribution will be calculated and summarized. This analysis is not part of the abbreviated scope.

Solicited AEs occurring on the day of vaccination and the following 7 days will be listed separately as well.

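### The same-grade rule for solicited AE duration splits one continuous reaction at each grade change, so an overall mean taken over those events can understate reaction length but never overstate it

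*SAP*

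**What the plan says.** Duration of solicited local and systemic AEs is part of the primary safety endpoint (Protocol 4.2.1, SAP 9.4). SAP 10.7.2.1.1 has it "defined as the sum consecutive days with local/systemic adverse events (days 1 to 8) for the same grade". Its only worked example is Fatigue at Grade 1 on Days 2, 3 and 7, which "will be counted as two separate events with the duration 2 days and 1 day". When the AE is still present on Day 9, the eCRF time from Day 9 to the end date "is added to the consecutive days as collected on the diary".

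SAP 12.7.1.2 plans "Duration (days) of solicited AEs, overall and for Grade 3 events", and Appendix 4 keeps one duration table, Table 14.3.2.6.1. The estimand in SAP 9.4 reads "The mean duration in days by group with standard deviation of solicited AEs (within the solicited period, total duration", and the parenthesis is not explained further. Protocol 10.3.5.1 adds: "The duration and severity of solicited AEs will be analyzed at subject level".

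SAP 10.7.1 says that an AE whose severity changes gets a fresh start date and its own CRF record.

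**The concern.** A reader of Table 14.3.2.6.1 will take the overall figure as how long reactions last. Under the same-grade condition, a reaction that builds and wanes without a symptom-free day is not one event but several short ones. Nothing in either document puts the pieces back together. If the pieces are averaged, a longer reaction that reaches a higher grade can appear shorter than a brief mild one. No other duration table is kept in the abbreviated scope to reveal this, and there is no control group to compare with.

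**Working it through.** **Inputs.** The run rule and its example come from SAP 10.7.2.1.1, the mean and SD from SAP 9.4, and the overall and Grade 3 rows from SAP 12.7.1.2. The documents contain no diary data, so every sequence below except the SAP's own example is illustrative.

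**Method.** A same-grade run is an unbroken series of days at one grade above 0. An any-grade episode is an unbroken series of days at any grade above 0. The SAP example is reproduced first.

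| Diary grades | Same-grade runs (days) | Mean of runs | Longest run | Sum of runs | Mean any-grade episode |
|---|---|---|---|---|---|
| SAP example: Grade 1 on Days 2, 3, 7 | 2, 1 | 1.5 | 2 | 3 | 1.5 |
| 1,2,2,1 | 1, 2, 1 | 1.33 | 2 | 4 | 4 |
| 2,2,1,1 | 2, 2 | 2.0 | 2 | 4 | 4 |
| 1,2,3,2,1 | 1, 1, 1, 1, 1 | 1.0 | 1 | 5 | 5 |
| 2,2,2,2 | 4 | 4 | 4 | 4 | 4 |
| 1,1 | 2 | 2 | 2 | 2 | 2 |

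The SAP example comes out the same with or without the same-grade condition, because its grade never changes. It shows how gaps are treated and is silent on grade changes; only the definition covers those. The order can reverse: 1,2,3,2,1 lasts 5 days and averages 1.0, while 1,1 lasts 2 days and averages 2.0.

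**Direction.** Splitting leaves total days unchanged and can only add events. With E episodes, D total days and c grade changes per episode on average, the event mean is D / [E(1 + c)], that is, the any-grade episode mean divided by (1 + c). Enumerating all 4^8 − 1 = 65,535 non-empty eight-day diaries agrees: the mean over same-grade runs is below the any-grade mean in 61,296, equal in 4,239 and above it in none. These counts are not frequencies to expect in the trial.

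**Dependence on the unit.** Take four diaries: 2,2,2,2 twice, 1,2,2,1 and 2,2,1,1.
- Averaged over events: 4, 4, 1, 2, 1, 2, 2, so n = 7, mean 16/7 = 2.29, SD 1.25.
- Summed per subject: 4, 4, 4, 4, so mean 4.0, SD 0.
- Check: grade changes are 0, 0, 2, 1, so c = 3/4 = 0.75 and 4.0/1.75 = 2.29.

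In the full enumeration the sum of runs equals the days at any grade in every diary. A per-subject sum therefore removes the effect. A per-subject mean or longest run does not: 1,2,2,1 gives 1.33 or 2.

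**After Day 8.** Take Grade 2 on Days 6 and 7, Grade 1 on Day 8, then eCRF Days 9 and 10 counted inclusively (an assumption). The later days join only the last diary run, giving events of 2 and 1 + 2 = 3 days, mean 2.5, against one 5-day episode. If the record rule in SAP 10.7.1 applies to solicited AEs continued on the eCRF, a severity change after Day 8 ends that record too, and the splitting continues.

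**Grade 3 row.** For 1,3,3,2, days at Grade 3 number 2 under either counting rule. If the row means the whole episode that reached Grade 3, the answer is 4.

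**The case against.** The strongest reply is that the harm is conditional. No text says that events are averaged. The protocol's reference to subject level, the subject-level heading of the endpoint column in SAP 9.4 and that section's mention of total duration all lean towards one figure per subject. The table shells, a separate document according to SAP 10.0 and not available here, may settle the unit. This stands in part. A reader might infer that the reported mean will be too short, and the documents do not support that. They equally do not say whether several runs in one subject are summed, averaged or reduced to the longest, and only the sum is free of the effect. Total duration may merely mean that days after Day 8 are included.

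A second reply is that splitting at a severity change matches the record convention in SAP 10.7.1 and so looks deliberate. That convention governs how records are captured. It does not make a same-grade run a sensible measure of overall reaction length.

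SAP 10.7.2 might seem to repair the split, since for related Grade 3 AEs reported on more than one day "the subject will be questioned to establish the total duration of the AE as exactly as possible". But it is limited to those events, and SAP 10.7.2.1.1 uses eCRF dates only from Day 9.

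A reader might also conclude that the gap rule is wrong and that total symptomatic days should replace episode length. Nothing here shows a defect in the gap rule, and total days is a different quantity.

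**Conclusion.** The concern holds in conditional form. Following the stated rule splits a continuous reaction at each grade change. An overall mean taken over the resulting events is too low or unchanged, never too high. The size in this trial cannot be given because c is unknown; it is zero if runs are summed per subject, and constant-grade episodes are unaffected under any unit.

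Two further inferences are not supported. One is that days after Day 8 escape the split, since SAP 10.7.1 may carry it forward. The other is that the Grade 3 row is safe: this is so only if the row counts days at Grade 3, and SAP 12.7.1.2 does not say.

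The matter is minor. The analysis is descriptive (SAP 12.0) in 129 enrolled subjects, the local and systemic solicited AE listings are retained, and no decision rule depends on it. It is still worth correcting, because the rule as written can misstate a primary safety summary.

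**What to change.** Amend SAP 10.7.2.1.1 as follows.

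- For the overall row, define an episode as consecutive days at Grade 1 or above whatever the grade, so that a grade change does not start a new event. Add the example 1,2,2,1 = one episode of 4 days.
- Keep the gap rule and its example unchanged: Grade 1 on Days 2, 3 and 7 remains two events of 2 days and 1 day.
- State the unit that is averaged, for example one value per subject, AE and dose, and how several episodes in one subject are combined. The choice matters: the SAP's own example gives 3 if summed, 2 if the longest is taken and 1.5 if averaged.
- For AEs ongoing after Day 8, chain consecutive eCRF records of the same AE and use the last end date.
- State whether the Grade 3 row means days at Grade 3 or whole episodes that reached Grade 3. Keep same-grade counting only in the first case.

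The cost is a few lines of SAP text and a small change to the derivation. No new data are needed.
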